7.0 ASSESSMENTS

Unless otherwise noted, the following assessments will be conducted at baseline, and at Weeks 4, 8, and 12, during the active intervention phase, as well as at 3- and 6-month post-intervention follow-up time points. A timeline of assessment administration is provided at the end of this section. Assessment tools have been selected to measure key constructs that we hypothesize will be impacted by the planned intervention, while ensuring that measures do not assess overlapping constructs.

7.1 Assessments conducted at Baseline only.

7.1.1 Enrollment (ENR-A) (2 min)

This form tracks the date of informed consent and collects several additional participant demographic variables (education, marital status, living arrangement, and distance from treatment program).

7.1.2 Demographics (DEM) (1 min)

Participants' basic demographics will be obtained at baseline and include sex, date of birth, and race/ethnicity.

7.1.3 Randomization (ENR-B)

This form is completed by research staff and documents inclusion/exclusion criteria and randomization information. It should be completed at the end of the baseline assessment.

7.1.4 DSM-IV Checklist (DSM) (5-10 min)

This is a semi-structured interview that provides current diagnosis for substance use disorders based on DSM-IV diagnostic criteria (Hudziak et al., 1993).

7.1.5 The Patient Health Questionnaire (PHQ) (10 minutes)

The PHQ will be used to assess co-occurring psychiatric problems, including major depression, social anxiety disorder, generalized anxiety disorder, PTSD, and ADHD (Blanco et al., Spitzer et al., 1999). Participants are asked to respond on a Likert scale the extent to which each of the criteria for a given disorder have been met, and an algorithm is applied to indicate presence/absence of a probable diagnosis.

7.1.6 The MicroCog[™] (15 min) (Powell et al., 2004)

Is a computer-administered battery of tests assessing neurocognitive functioning? Five subtests are selected for use in this study in the following domains: memory, sustained focus attention, inductive reasoning, concept formation and cognitive flexibility, and visuoperceptual analysis. Differential attention, memory, or spatial processing may impact outcomes of the cognitive-behavioral based TES intervention.

7.2 Planned Assessment for Effectiveness Analyses

7.2.1 Substance Use Outcomes based on Urine Toxicology, Breath Alcohol, & Self-Report (10 min)

Urinalysis and breathalyzer will occur at the baseline visit, twice per week for 12 weeks of the active study phase, and at the 3-month and 6-month follow up visits (procedures will coincide with the timing of planned contingency management procedures designed to reinforce drug abstinence). Each urine sample will be tested for the presence of 10 drugs: cocaine, opiates 2000 ng (includes morphine, codeine, and heroin), amphetamines, cannabinoids (THC), methamphetamines, benzodiazepines, oxycodone, methadone, barbiturates, and MDMA. A

breathalyzer will be used to screen for blood alcohol concentration (BAC), scored as negative versus positive for blood alcohol according to the standard cutoff. Participants whose BAC is above a .08 (standard legal limit) will be asked to wait to complete any additional assessments until their BAC is below .08 to ensure that participants are not intoxicated during the completion of the assessment measures. The intoxication event should be recorded in the progress notes. Research staff will use clinical judgment as whether participants can reasonably complete assessments with BAC levels above .01 but below .08.

Although it is encouraged that urine collections be observed by a same-sex observer to ensure the integrity of samples, it is recognized that this will not be possible in all situations and settings. Two validity checks of urine screens will be employed. First, a valid urine sample must fall within standard temperature ranges (e.g. > 90 and < 100 degrees Fahrenheit) as indicated by temperature strips located on the test cup. A further validity check will be provided by a commercially available adulterant test strip that indicates normal ranges for creatinine, pH (at minimum), nitrate, glutaraldehyde, specific gravity, bleach and pyridinium chloromate in human urine. Participants whose urine does not pass both of the validity checks will be offered the opportunity to provide a second sample. The second sample will need to be validated before urinary drug screen analysis. Urinalysis is never to be performed before a sample is validated and confirmed negative for adulterants. If the participant refuses to offer a sample, then the urinary drug screen will be counted as missing for that day (and positive for purposes of incentive procedures). Missing urine or alcohol samples will override a self-report of no substance use.

The timeline follow-back calendar assessment (TLFB; Sobell & Sobell, 1992) will be completed once per week during the treatment phase to assess self-reported substance use since the time of the last assessment (including time since last assessment during follow-up time points). The TLFB assessment uses calendars to obtain estimates of days of alcohol use, including standardized drink quantities, days of heavy drinking, and other substances (cocaine, opiates, amphetamines, methamphetamines, ecstasy, benzodiazapines, barbiturates, oxycodone/ oxycontin, methadone, and marijuana), using memory aids to enhance recall (e.g., patterns of use, key dates). The TLFB has good psychometric properties, including test-retest measurement with multiple populations and content, criterion, and construct validity across multiple related measures (Sobell & Sobell, 2000). A summary of information obtained from the TLFB procedure will be generated from the calendars.

7.2.2 Risk Behaviors Scale (RBS) (5 min) (Booth et al., 1993)

This questionnaire assesses sexual behavior and has been found to be a valid and reliable measure of HIV risk behavior.

7.2.3 Social Adjustment Scale – Self Report (SAS-SR) (10 min) (Weissman, 1999)

This questionnaire consists of 54-items assessing six social role areas (work, social and leisure activities, family relationship, marital relationship, parental role, and role within the family unit). The SAS-SR is completed only at baseline, week 12, and 3- and 6-month follow-up. The SAS-SR has been widely used, with normative data for comparative purposes.

7.2.4 Brief Symptom Inventory (BSI) (3 min) (Derogatis & Melisaratos, 1983)

The Brief Symptom Inventory is a brief, 18-item self-report measure of severity of psychiatric symptoms, derived from the longer SCL-90. It yields a global severity index (GSI), and three clinical subscales, somatization, depression, and anxiety, and has been shown to have good reliability and validity in a broad range of patient populations. This will be assessed at baseline, and weeks 4, 8, 12, and 3- and 6-month follow-up.

7.2.5 Fagerstrom Test for Nicotine Dependence (FND) (2 mins)

The 6-item FND provides an ordinal measure of nicotine dependence related to cigarette smoking, including quantity of cigarette consumption, severity, and compulsion to use. An additional question assesses the use of medication to help stop smoking.

7.2.6 Participant Feedback Survey (5 min)

This scale consists of five questions asking participants to rate how 1) interesting, 2) easy to understand, and 3) useful their psychosocial intervention with counselor and computer (for those in the test arm of the trial) was, and the 4) extent to which the intervention provided them with novel information and asks 5) how satisfied they were with their substance abuse treatment when combined with the psychosocial intervention they experienced (ranging from 0-10, anchored at "not at all" to "very much"). They will also be asked to provide information related to these same issues in Free Response format (e.g., qualitative, prose-like comments). Separate forms will be used for each study condition. This measure will be completed only at weeks 4, 8 and 12.

7.2.7 Coping Strategies Scale (CSS) – Brief Version (4 min) (Litt et al., 2003)

This 23-item questionnaire (originally adapted from the Processes of Change questionnaire, Prochaska et al., 1988) assesses change processes and skills taught in coping-skills treatment, such as problem solving and dealing with urges to use substances of abuse. Participants will rate on a 4-point scale their frequency of using each strategy to help avoid substance use. Total coping is measured by taking the mean across all 23 items (internal reliability from multiple samples α =.83 to .87). The CSS yields 4 subscales: active–behavioral, active–cognitive, avoidant–behavioral, and avoidant–cognitive. This scale will be of primary importance to assess the extent to which the Therapeutic Education System (TES) impacts the development of coping skills, a hypothesized mediating variable that, in turn, impacts substance use behavior. This measure will be completed only at baseline, week 12 and at the 3- and 6-month follow-up time points.

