4.2 Secondary Objectives

- To evaluate the relative effectiveness of TAU vs. the modified TAU+TES interventions on several secondary outcome measures, including measures of HIV risk behavior (using the Risk Behavior Survey; Booth et al., 1993), psychosocial functioning (in areas of criminal activity, health status improvement, psychological status, family/social relationships, and employment, using the SAS-SR, Weissman, 1999; NMS; and BSI, Derogatis & Melisaratos, 1983) and treatment acceptability (based on participant feedback). (See Section 7 for planned list of assessments).
- To evaluate if improved outcomes are maintained at 3 and 6 months postintervention.
- To perform a comprehensive economic analysis of including TES in TAU to inform decisions regarding adoption of this new therapeutic tool (assessing incremental costs per increased abstinence time and quality adjusted life year). The economic analyses are clinically important, as even if the computerized intervention is shown to be effective, it may not be adopted in community-based treatment programs unless it is shown to be cost-effective due to the considerable financial constraints in such treatment settings.
- To examine coping skills acquisition as a treatment process factor that may underlie changes observed during treatment. These analyses will allow an assessment of the extent to which TES impacts the development of coping skills, a hypothesized mediating variable that, in turn, impacts substance use behavior.
- To conduct exploratory analyses to assess (a) the effect of dose of TES exposure on drug abstinence and retention outcomes, (b) whether various sub-groups of participants have differential outcomes in drug abstinence and treatment retention across treatment conditions (e.g. stimulant vs. non-stimulant users; gender) and (c) whether various demographic variables, as well as baseline psychological and other history variables predict successful outcomes across treatment conditions in reducing substance use and promoting treatment retention.

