TES also includes an electronic reporting system (with appropriate password protection and an encrypted Internet connection via Secure Sockets Layer, the de facto standard for securing communications on the World Wide Web) summarizing patients' activity using TES. This feature allows the research staff to provide therapists reports on participant activity with TES and integrate participants' use of TES into their counseling sessions with the patient. In the planned study, counselors will be trained on how to how to help participants organize their customized TES plan based on unique needs. Thus, TES is a tool that counselors can use to extend their therapeutic efforts. We will track the extent to which counselors discuss TES with their clients in individual sessions.

CORE Modules within Therapeutic Education System (TES)

A total of 32 Modules will represent CORE modules within TES in this trial, and participants will be asked to complete these modules within weeks 1-8 of the trial (4 modules per week for 8 weeks, approx. 20-30 minutes per module).

- 1. Training Module
- 2. What is Functional Analysis?
- 3. Conducting a Functional Analysis
- 4. Self-Management Planning
- 5. Introduction to Problem Solving
- 6. Effective Problem Solving

- 7. Drug Refusal Skills Training
- 8. Seemingly Irrelevant Decisions
- 9. Coping with Thoughts about Using
- 10. Awareness of Negative Thinking
- 11. Managing Negative Thinking
- 12. Managing Thoughts about Using
- 13. Managing Negative Moods and Depression
- 14. Decision-Making Skills
- 15. Increasing Self-Confidence in Decision-Making
- 16. Introduction to Assertiveness
- 17. How to Express Oneself in an Assertive Manner
- 18. Introduction to Giving Criticism
- 19. Steps for Giving Constructive Criticism
- 20. Receiving Criticism
- 21. Giving and Receiving Compliments
- 22. Communication Skills
- 23. Nonverbal Communication
- 24. Social Recreational Counseling
- 25. Attentive Listening
- 26. Sharing Feelings
- 27. HIV and AIDS
- 28. Sexually Transmitted Infections (STIs)
- 29. Sexual Transmission of HIV and STIs
- 30. Drug Use, HIV and Hepatitis
- 31. Identifying/Managing Triggers for Risky Sex
- 32. Identifying/Managing Triggers for Risky Drug Use

OPTIONAL Modules within Therapeutic Education System

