14.1.2 Secondary Hypotheses

- We hypothesize that differential outcomes in drug abstinence observed across groups during treatment will continue to be observed at the 3- and 6- month follow-up time points.
- We expect that psychosocial functioning will improve in the group that received the modified TAU+TES at 3- and 6-month follow-up time points relative to the TAU alone condition.
- We hypothesize that the modified TAU+TES intervention will be cost-effective relative to TAU from both the health care sector and CTP program perspectives at the 3- and 6-month follow-up time points.
- We hypothesize that individuals in modified TAU+TES will show significant increases in coping skills acquisition (as measured via the Coping Strategies Scale) relative to TAU at end of treatment and 3- and 6-month time points, and we expect that coping skills will be shown to serve as a mediator substance use outcomes.

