14.4.1 Statistical Methods and Sample Size Considerations for Primary Abstinence Measure

Let y_{it} denote the indicator of abstinence for participant i (i=1,...,n) during half-week t (t=1,...,24). The vector of outcomes for a participant, $y_i = (y_{i1}, ..., y_{i24})$, constitutes the primary outcome measure of abstinence. The precise definition of half-week t is the time between the (t-1)th urine collection and the t^{th} urine collection. For example, consider a participant whose third and fourth urine collections fall on days 8 and 11 of the treatment phase of the study. The fourth half-week would then comprise TLFB self report data from days 8 through 10 confirmed by the urinalysis on day 11. To be considered abstinent in the fourth half-week ($y_{i4} = 1$), the participant must report no drug or heavy alcohol use on days 8, 9 and 10 and the urine sample collected on day 11 must be negative. If that urine sample is missing for any reason and no use was reported via TLFB, then the indicator of abstinence for the participant is missing for the fourth half-week. If on days 8-10 there is at least one self-reported day of heavy drinking or drug use (i.e., positive self report) or the urinalysis is positive, then the participant is considered not abstinent ($y_{i4} = 0$).

The primary outcome analysis of abstinence will evaluate whether assignment to TAU+TES is associated with more abstinence in the last four weeks of the treatment phase of the study compared with those assigned to TAU. Previous CTN studies have noted that after a certain period of time (approximately four weeks), the effect of both TAU and contingency management therapies stabilize. To minimize the possibility of a time by treatment interaction affecting the primary comparison between the two treatment groups, we will model all 24 half-weeks, but only test for a treatment difference during the last eight half-weeks of the 12-week treatment phase.

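### For on-treatment abstinence, the only in-treatment measure of coping skills after baseline comes at the end of the tested weeks 9-12, so mediation there cannot be told apart from coping that follows abstinence

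*Protocol*

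**What the plan says.** - **When coping is measured.** Section 7.2.7 states: "This measure will be completed only at baseline, week 12 and at the 3- and 6-month follow-up time points". The assessment schedule at the end of section 7 agrees, with no CSS entry at week 4 or week 8.
- **What it is for.** The same section calls coping "a hypothesized mediating variable that, in turn, impacts substance use behavior". Section 4.2 gives the objective: "To examine coping skills acquisition as a treatment process factor that may underlie changes observed during treatment". Section 14.1.2 adds: "we expect that coping skills will be shown to serve as a mediator substance use outcomes". It sets the comparison of coping between arms "relative to TAU at end of treatment and 3- and 6-month time points".
- **When abstinence is tested.** Section 14.4.1 models all 24 half-weeks but will "only test for a treatment difference during the last eight half-weeks of the 12-week treatment phase".
- **When the core skills are taught.** For the 32 core modules, section 9.4.1.2 says: "participants will be asked to complete these modules within weeks 1-8 of the trial".
- **Which visits already exist.** Unless stated otherwise, section 7.0 says "the following assessments will be conducted at baseline, and at Weeks 4, 8, and 12", plus the two follow-ups. The schedule shows the RBS, BSI, EuroQol and NMS at weeks 4 and 8.

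**The concern.** A mediator has to be measured before the outcome it is meant to explain. Here the skills are taught in weeks 1-8 and the effect on abstinence is tested in weeks 9-12. The informative time for a coping measurement is therefore about week 8, and none is scheduled. The first one after baseline comes when the tested window is closing.

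The reverse direction is plausible in this trial. Participants rate on the CSS how often they use each strategy to avoid substance use, and someone who is staying abstinent may well report more of it. The TAU+TES arm also earns prize draws for negative samples, which TAU does not, so abstinence can rise in that arm without any gain in skill. Arm, abstinence and week-12 CSS could then all be associated although coping caused nothing. At stake is the reading of one secondary objective, namely whether a positive mediation result for on-treatment abstinence would mean what section 4.2 wants it to mean.

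**Working it through.** The protocol gives no power, effect size or other figure for the mediation analysis, so there is nothing of its own to reproduce. The check has two parts: timing, and an illustration of size.

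**Timing**

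| Event | When | Source |
|---|---|---|
| Core modules | weeks 1-8 (half-weeks 1-16) | 9.4.1.2 |
| CSS | baseline, week 12, 3 and 6 months | 7.2.7, schedule |
| Tested abstinence | half-weeks 17-24 (weeks 9-12) | 14.4.1 |
| Other scales | also weeks 4 and 8 | 7.0, schedule |

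Week 12 consists of half-weeks 23 and 24. Of the eight tested half-weeks, 17 to 22 (six) are complete before week 12 starts, and 23 to 24 (two) are concurrent with it. None clearly follows a post-randomisation CSS. With a CSS at week 8, all eight would follow one. Using change from baseline does not help, because change from baseline to week 12 builds up over the same weeks as the outcome.

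**Size, if coping is only a consequence**

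Inputs:
- N = 500, 250 per arm (section 14.4).
- Arm effect on abstinence d = 0.2 or 0.33 SD. The upper value is (3.6 - 2.4)/3.63 = 0.33, from the abstinent weeks in section 14.14.4. The lower value is assumed.
- Abstinence-to-CSS correlation b = 0.3 or 0.5. Both are assumed, since the protocol gives none.

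Model: Y = d·arm + e and CSS = b·Y + √(1-b²)·e′, with unit-variance errors. The true mediated effect is zero. Mediation is declared when arm→CSS and CSS→Y given arm are both significant at 0.05.

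The arm→CSS effect is b·d, with SE = √(4/500) = 0.0894. The CSS→Y coefficient given arm is b, which at these values is almost always significant at N = 500. The false-mediation rate is therefore nearly the power of the arm→CSS test, Φ(b·d/0.0894 - 1.96), ignoring the small opposite tail:

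| d | b | b·d/SE | Formula | Simulated, two runs of 2,000 trials |
|---|---|---|---|---|
| 0.2 | 0.3 | 0.67 | 10% | 11%, 10% |
| 0.2 | 0.5 | 1.12 | 20% | 20%, 19% |
| 0.33 | 0.3 | 1.11 | 20% | 21%, 20% |
| 0.33 | 0.5 | 1.85 | 45% | 45%, 45% |

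The apparent share mediated is (b·d)·b/d = b², that is 9% at b = 0.3 and 25% at b = 0.5, when the truth is zero. If 30% of CSS values were missing completely at random (an assumption, N = 350), the simulated range would be about 8% to 33%. A separate run of 1,000 trials per cell with stronger assumptions (d = 0.22-0.30, b = 0.5-0.7) gave 24% to 67%.

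**The case against.** Several objections have force.

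- **Scope.** A reader might infer that the whole mediation objective is beyond rescue. The protocol does not support that. Section 14.1.2 speaks of substance use outcomes in general and expects abstinence differences at 3 and 6 months. Urine is tested at both follow-ups, and the TLFB covers the interval since the last assessment. Week-12 CSS precedes those outcomes, so temporal order is available there, although abstinence during treatment can still confound the relation.
- **Completeness of the outcome.** A reader might say that all 24 half-weeks are over when the CSS is taken. That is slightly too strong, because the last two are concurrent with week 12.
- **Emphasis.** Section 7.2.7 attaches primary importance to whether TES changes coping skills. That is a randomised comparison, which week-12 CSS against baseline can address. Mediation appears there as a description of the variable, so the protocol should not be read as giving mediation that rank.
- **Magnitude.** The 0.33 SD concerns abstinent weeks over the full 12 weeks and comes from the economic section, whereas the target here is a binary outcome in weeks 9-12. The correlations are assumed. The model leaves out baseline CSS; including it would change the rates but would not restore the time order. The figures show what happens if coping has no effect, not how likely that is.
- **Modules against prizes.** A reader might infer that the trial would wrongly credit the modules and so mislead adoption, or that an earlier CSS would settle the matter. Neither follows. The protocol tests modules and incentives as one package and rests adoption on its effectiveness and cost-effectiveness. A week-8 CSS would itself come after eight weeks of incentivised abstinence.
- **Weight.** This is a secondary objective, section 14.10 promises cautious interpretation of secondary analyses, and the mediation model may be set out in a statistical analysis plan that is not at hand.

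What remains is the timing. No analysis plan can supply a measurement that was never scheduled.

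**Conclusion.** The point holds for on-treatment abstinence. The only post-baseline CSS in the treatment phase falls at the end of the tested window, so a significant mediation result for weeks 9-12 could not show that coping came first. The part of section 4.2 that concerns change during treatment is therefore not served by the schedule. Mediation of 3- and 6-month outcomes keeps its time order, subject to confounding by earlier abstinence, and both co-primary tests are untouched.

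The timing conclusion rests on the protocol's schedule alone. The rate of about 10%-45% is an illustration: it depends on the assumed correlations and arm effects, on complete CSS data and on coping having no effect at all. It should not be quoted as this trial's error rate. Because the remedy is cheap, the change is worth making as a modest design improvement.

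**What to change.** **Preferred.** Add the CSS at the existing week 8 assessment, with week 4 optional. Relate week-8 CSS, adjusted for baseline CSS and for abstinence up to week 8, to abstinence in half-weeks 17-24. State two limits: the adjustment may remove mediation that acts through early abstinence, and the change improves temporal order without separating modules from incentives. At 4 minutes per administration, the cost is 4 minutes per participant for week 8 alone, or 8 minutes with week 4. Both visits are already held and compensated (section 9.7). The schedule table and section 7.2.7 need a matching edit.

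**Otherwise.** Restrict the mediation claim to week-12 CSS and abstinence at 3 and 6 months, adjusted for abstinence in weeks 9-12. Describe any on-treatment relation as an association, and reword the objective in section 4.2 to match. This costs wording only.
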